7.1.2.6 Chest Radiograph

A chest radiograph will be performed, as clinically indicated, to evaluate for fungal infection.

7.1.2.7 IV Study Drug Administration/Infusion Site Examination

- The collection of blood specimens for safety labs and PK trough levels should preferably occur prior to the administration of POS IV solution.
- The subject's body weight at Baseline will be used to calculate all IV doses
- IV infusions should be administered via a central line at approximately the same time each day. On the first day of IV dosing there is a loading period during which 2 doses are given, separated by 12 hours. Subsequently, a single dose is given once daily. For the third dose, the dose should be timed to be given approximately 24 hours after the initial loading dose (i.e., approximately 12 hours after the second loading dose). All subsequent IV doses should be administered approximately 24 hours apart. If for any reason the timing of the medication needs to be adjusted after the first dose, the dose time may be adjusted by +/-3 hours.
- The infusion site should be examined prior to and at the end of the infusion according to local standard of care. Any adverse events observed at the infusion site or during the infusion will be recorded on the eCRF.

7.1.2.8 Oral Study Drug Administration (PFS)

- The collection of blood specimens should preferably occur prior to the oral administration of POS PFS.

- A subject's body weight should be measured within 3 days prior to the first day of POS PFS treatment. The weight measured will be used to calculate all subsequent doses of POS PFS treatment.
- The POS PFS dose may be administered by oral syringe or via a feeding tube and should be prepared and administered using the Sponsor supplies as outlined in the Pharmacy Manual. Refer to the Pharmacy Manual for additional details on allowed dosing devices.
- Doses of POS PFS should be administered 24 hours apart at approximately the same time each day. If for any reason, the timing of the medication needs to be adjusted after the first dose, the dose time may be adjusted by +/- 3 hours.
- The Study Medication/Food Diary must be completed for every dose of PFS. If treatment is given as an outpatient, the subject or the subject's guardian or caretaker will complete the study medication/food diary on a daily basis. The diary will be collected and entered by site study staff at the visits outlined in the trial flow chart (Section 6.0).
- Subjects who vomit within 30 minutes of POS PFS administration should be given a replacement dose as soon as possible. Repeated episodes of vomiting should be recorded on the Adverse Event (AE) eCRF and the Dosing eCRF.
- Subjects should be observed for approximately 30 minutes after the first dose of PFS for tolerance. During this time, a palatability assessment should be performed as outlined in Section 7.1.2.9.

7.1.2.8.1 Outpatient Administration of Oral Study Medication (PFS)

It is preferred that the subject be administered their first dose of PFS before leaving the hospital so the patient and caregiver have an opportunity to observe or be observed preparing the first oral dose (PFS) for administration. If the investigator determines that the subject is able to be discharged from the hospital and will be able to continue treatment with POS PFS at home, the investigator should take the following steps:

- Refer to the Trial Flow Chart and determine the number of days until the next PK collection timepoint and schedule the out-patient appointment (allowing enough time to perform PK blood sampling predose (0 hour), 2, and 4 hours post-dose).
- Direct IVRS to dispense enough doses (including replacement doses if the subject is at risk of vomiting) for the subject to take home with them to last until their next clinical visit.
- Instruct the subject not to take their daily dose of POS PFS prior to their scheduled appointment on clinic visit days. On the clinic visit days, doses of PFS should be administered in the clinic after the pre-dose PK blood sample is collected and recorded in the study medication/food diary.
- Provide the subject/parent/caregiver with the study medication/food diary and the Palatability Assessment form and instruct them on how to complete both forms.

- Instruct the subject/parent/caregiver to bring all medication (including empty packages), the palatability assessment form and the study medication/food diary with them to all office visits.

These steps need to be repeated at every outpatient visit.

7.1.2.9 Assessment of Palatability (Taste)

All subjects will rate the palatability of the PFS formulation at three times during the PFS treatment phase of the study:

- Immediately after the first oral dose (POS PFS).
- Approximately 3-5 days later immediately after the subject has taken their oral dose.
- At the End of Treatment (EOT), immediately after the last dose of oral treatment.

The palatability assessment questionnaire that will be used can be found in the Administrative Site Binder.

The palatability assessment should be completed for all subjects regardless of age or condition. The paper form may be completed by the subject, reported by the patient to an observer (caregiver or parent), or completed as observed by a parent/primary caretaker, nurse or member of the trial staff.

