3.2 Secondary Objective(s) & Hypothesis(es)

- 1) **Objective:** To evaluate the safety and tolerability of POS IV solution and POS PFS administered to immunocompromised pediatric subjects (ages 2 years to 17 years) with neutropenia or expected neutropenia

Estimation: Safety parameters will be summarized for each age group and dose cohort.

3.3 Exploratory Objectives:

- 1) **Objective:** To evaluate the palatability and acceptability of POS PFS
- 2) **Objective:** To evaluate the PK of sulfobutylether-beta-cyclodextrin (SBE β CD)

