8.2.4 Other Analyses

Compliance with study medication, including palatability/acceptability of the POS PFS formulation, will be summarized by age and treatment group.

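### Palatability (taste) is to be assessed even for doses given by feeding tube and is summarised without regard to route or rater, so the exploratory taste summary can mix ratings that do not measure the same thing

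*Combined protocol and SAP*

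**What the plan says.** The first exploratory objective in Section 3.3 is "To evaluate the palatability and acceptability of POS PFS". Section 4.2.4.4 plans the assessment in all subjects.

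On route, Section 7.1.2.8 states: "The POS PFS dose may be administered by oral syringe or via a feeding tube". The same section asks for about 30 minutes of observation after the first PFS dose and adds: "During this time, a palatability assessment should be performed as outlined in Section 7.1.2.9". It makes no exception for a tube-given dose.

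On who is assessed, Section 7.1.2.9 begins: "All subjects will rate the palatability of the PFS formulation at three times during the PFS treatment phase of the study". The three times are after the first oral dose, about 3 to 5 days later, and at end of treatment. The section then says: "The palatability assessment should be completed for all subjects regardless of age or condition".

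On who rates, the same section allows the child to complete the form, the child to report to a caregiver or parent, or the form to be "completed as observed by a parent/primary caretaker, nurse or member of the trial staff". It sets no rule by age and does not ask for the same rater at all three times.

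On analysis, Section 8.2.4 is the only text: "palatability/acceptability of the POS PFS formulation, will be summarized by age and treatment group". Section 8.1 says that no separate SAP will be issued.

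**The concern.** Taste can be rated meaningfully only when the dose passes through the mouth. The plan permits a route that largely bypasses taste and then, by an explicit rule, requires the taste assessment whatever the child's condition. Nothing in the analysis text removes or labels those ratings.

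The rater raises a second, separate issue. Age Group 1 is 2 to <7 years and Age Group 2 is 7 to 17 years, so it is reasonable to expect more proxy rating in the younger group. If proxies and children score differently, a table by age shows age and rater together.

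At stake is how the exploratory palatability result can be read. Section 4.1.1 presents PFS as an age-appropriate formulation, and the only taste evidence it cites comes from healthy adults. This table would therefore be the paediatric evidence on taste. Nothing in the primary PK objective depends on it.

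**Working it through.** **The texts side by side.**

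1. Section 7.1.2.8: tube dosing is permitted, and an assessment follows the first dose.
2. Section 7.1.2.9: the assessment measures taste and covers every subject regardless of condition, at three times.
3. Section 5.7: the diary contents listed are dose time, type of meal and timing of the meal. Route is not listed.
4. Section 8.2.4: the summary is by age and treatment group. Neither route nor rater appears.

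A child dosed by tube at an assessment time therefore enters the taste table under rule 2 and is not separated out under rule 4. The same holds for a proxy-rated child within an age group.

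**The plan's own figure.** There is none to reproduce. The documents state no palatability rate, tube share or rater mix, and Section 8.2.5 says that the sample size has no formal power basis.

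**Illustrations on assumed inputs.** These show only what size is possible. None of the inputs comes from the documents unless stated.

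*Tube-given doses.* Let t be the share of children dosed by mouth who rate the taste acceptable, f the tube-dosed share of those scored, and a the share of tube-dosed children recorded as acceptable.

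Reported share = (1 − f) × t + f × a

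Take t = 0.70:
- f = 0.05: a = 0 gives 0.95 × 0.70 = 0.665; a = 1 gives 0.665 + 0.05 = 0.715.
- f = 0.30: a = 0 gives 0.70 × 0.70 = 0.49; a = 1 gives 0.49 + 0.30 = 0.79.

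A true 70% could thus be reported as anything from 49% to 79%, a shift of −21 to +9 points. Even the direction is not fixed.

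*Rater mix.* Let p1 and p2 be the proxy-rated shares in Age Groups 1 and 2, and g the proxy-versus-self gap. With no true age difference:

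Apparent age difference = (p1 − p2) × g

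- p1 = 0.70, p2 = 0.30, g = 0.10: 0.40 × 0.10 = 0.04.
- p1 = 1.00, p2 = 0.10, g = 0.30: 0.90 × 0.30 = 0.27.

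The apparent difference runs from 4 to 27 points.

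*Chance that a cell is affected.* Assume 12 PFS-treated children in an age-by-dose cell. Twelve is the minimum PK-evaluable number per age group in Dose Cohort #3; the number who will reach PFS is not stated. The chance of at least one tube-dosed child is 1 − (1 − f)^12: 46% at f = 0.05, 72% at f = 0.10 and 93% at f = 0.20.

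**The case against.** The case on the other side is substantial, and most of it stands as a limit on size.

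- **Tube use is permitted, not shown.** A reader might infer that the taste scores do include children who never tasted the drug. The documents do not support that: they give no tube-use figure. Section 2.1 starts PFS in children who are willing and able to tolerate oral treatment and lets others stay on IV, which makes tube use less likely. Nor need a tube-dosed child be dosed that way at all three assessments.
- **The forms are not in the documents.** The questionnaire is in the Administrative Site Binder, and Section 7.1.2.8 refers to a Pharmacy Manual and a Dosing eCRF. Any of these may already record route or rater, or offer a not-applicable answer. That would ease the fix, but Section 8.2.4 still uses none of it.
- **No formal comparison is planned.** A reader might infer that the plan will draw a confounded conclusion about age, or about change from first dose to end of treatment. Section 8.2.4 specifies only a descriptive summary. Proxy rating of two-year-olds is unavoidable, and tabulating by age already separates the groups likely to differ most in rater.
- **Small cells are noisy anyway.** With 12 children and a true 70%, the standard error is √(0.70 × 0.30 / 12) = √0.0175 = 0.132, about 13 points, so many of the shifts above lie within sampling error. This lowers the practical weight, but misclassification does not average out when cells are pooled.
- **Table 1 cannot size the effect.** Its PFS counts of 5 to 10 are PK-evaluable subjects in Dose Cohorts #1 and #2, which have completed enrolment. They are not the palatability population.
- **Acceptability is also an objective.** Keeping tube-dosed children on the form can serve that half. This is a reason to report them separately, not to drop them.

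**Conclusion.** The point holds as a low-weight flaw in an exploratory measure. A stated rule, not merely a silence, brings any tube-given dose into a taste assessment, and the analysis text neither excludes such doses nor separates self from proxy ratings. Descriptive differences by age could therefore partly reflect who completed the form.

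The size is unknown. The ranges of −21 to +9 points for tube dosing and 4 to 27 points for rater mix rest wholly on assumed shares, and should not be read as estimates of what happened in this trial. If no child is dosed by tube at an assessment time, the first part has no effect. If proxies and children score alike, the second has none. The primary PK endpoint, the safety analysis and dose selection are untouched.

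**What to change.** Apply the following prospectively in Dose Cohort #3, which is still to enrol at least 36 subjects.

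- **Section 7.1.2.9:** for a tube-given dose, mark taste as *not applicable – tube*. Record route (oral syringe or tube) and rater (self, reported through an observer, or observed by another) at each of the three assessments, if the existing forms do not already do so. Keeping the same rater for a child is a preference only, where feasible: Section 7.1.2.8.1 prefers the first dose in hospital and then sends the form home with the family.
- **Section 8.2.4:** summarise taste only for doses taken by mouth, by age and treatment group, and show self and proxy ratings separately as description. Report tube administration separately under acceptability.
- **Dose Cohorts #1 and #2:** use route and rater where they were recorded; otherwise state the limitation.

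The cost is at most two form fields, a few sentences of protocol and SAP text, and slightly fewer taste scores. No dosing or clinical rule changes.

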7.1.2.10 Adverse Event Monitoring

The monitoring for Adverse Events will occur at the visits outlined in the Trial Flow Chart following the guidelines in Section 7.2.

7.1.2.11 Survival Assessment

A survival assessment (if the subject is alive or dead) will be performed between Day 90 and Day 110 and will be recorded on the eCRF. In the event of death, the cause and date of death will also be recorded. This assessment can occur by telephone or by using medical records.

7.1.3 Laboratory Procedures/Assessments

Details regarding specific laboratory procedures/assessments to be performed in this trial are provided below. The total amount of blood/tissue to be drawn/collected over the course of the trial (from pre-trial to post-trial visits), including approximate blood/tissue volumes drawn/collected by visit and by sample type per subject can be found in Appendix 12.4.

7.1.3.1 Laboratory Safety Evaluations (Hematology, Chemistry, Urinalysis & Other

Laboratory tests for hematology, chemistry and urinalysis are specified in [Table 8](#). These safety lab tests will be performed locally. The timing for these assessments are outlined in the Trial Flow Chart (Section 6.0).

- If the Baseline and Day 1 visits are combined, clinical lab tests should be drawn prior to the administration of study treatment.
- Blood specimens may be drawn either peripherally or via central venous catheter.
- If during the trial any laboratory result is outside the reference range and is considered clinically significant by the investigator, the test should be repeated at appropriate time intervals until it returns to baseline or becomes a clinically insignificant finding.
- If clinically indicated, safety lab tests may be repeated more often to evaluate clinical symptoms of AEs and must be followed until stabilization or return to baseline.

Table 8 Laboratory Tests

Hematology	Chemistry	Other
Hematocrit	Albumin	Serum β -human chorionic gonadotropin (β -hCG) ¹
Hemoglobin	Alkaline phosphatase	
Platelet count	Alanine aminotransferase (ALT)	
WBC (total and differential)	Aspartate aminotransferase (AST)	
Absolute neutrophil count (ANC)	Bicarbonate	
	Calcium	
	Chloride	
	Creatinine	
	Glucose	
	Potassium	
	Sodium	
	Total Bilirubin	
	Direct bilirubin, if total bilirubin is elevated above the upper limit of normal	
	Total protein	
	Blood urea nitrogen	
	Magnesium	

If possible, lab samples should be collected in the fasting state (after an overnight fast for morning sample).

7.1.3.2 Pharmacokinetic/Pharmacodynamic Evaluations

Plasma posaconazole concentration data will be used to estimate the following PK parameters:

- C_{avg} : Average steady-state plasma concentration
- C_{min} : POS trough level immediately before a subject receives the dose on the day specified in the protocol
- C_{max} : Maximum plasma concentration
- T_{max} : Time of maximum plasma concentration
- AUC: Area under the plasma concentration versus time curve
- CL: Total body clearance
- CL/F: Apparent total body clearance

The current blood sampling schedule is an optimized schedule based on the adult steady-state PK data. For patients receiving IV therapy, if all blood samples can be collected at steady-state as scheduled, the steady-state AUC will be calculated using the non-compartmental trapezoidal method. The C_{avg} will be calculated by dividing the AUC with dosing interval. For patient receiving PFS, since sparse PK samples are collected for outpatients, a population PK analysis will be conducted and model-predicted plasma concentration-time profiles will be used to determine C_{avg} .

Plasma sulfobutylether-beta-cyclodextrin-containing (SBE β CD) concentration data will be used to estimate the following PK parameters:

- C_{max} : Maximum plasma concentration
- T_{max} : Time of maximum plasma concentration
- AUC: Area under the plasma concentration versus time curve

7.1.3.2.1 Blood Collection for Plasma Posaconazole Levels of MK-5592

Sample collection, storage, and shipment instructions for plasma samples will be provided in the operations/laboratory manual.

7.1.3.3 Future Biomedical Research

The following specimens are to be obtained as part of Future Biomedical Research:

- Buccal swabs for genomics use

7.1.4 Other Procedures

7.1.4.1 Withdrawal/Discontinuation

When a subject discontinues/withdraws from participation in the trial, all applicable activities scheduled for the final trial visit (EOT) should be performed at the time of discontinuation. Any adverse events which are present at the time of discontinuation/withdrawal should be followed in accordance with the safety requirements outlined in Section 7.2 - Assessing and Recording Adverse Events. A PK trough sample should be collected approximately 24 hours after the last dose, and all other safety assessments will be performed. The investigator or trial coordinator must notify the Sponsor when a subject has been discontinued/withdrawn from the trial. If a subject discontinues for any reason at any time during the course of the trial, the subject may be asked to return to the clinic (or be contacted) for the End of Trial (EOT) approximately 72 hours after the last dose of trial drug is administered to have the applicable procedures conducted. However, the investigator may decide to perform the End of Trial procedures at the time of discontinuation or as soon as possible after discontinuation.

7.1.4.1.1 Withdrawal From Future Biomedical Research

Subjects may withdraw their consent for Future Biomedical Research and have their specimens and all derivatives destroyed. Subjects may withdraw consent at any time by contacting the principal investigator for the main trial. If medical records for the main trial are still available, the investigator will contact the Sponsor using the designated mailbox ([contact]), and a form will be provided by the Sponsor to obtain appropriate information to complete specimen withdrawal. Subsequently, the subject's specimens will be removed from the biorepository and be destroyed. A letter will be sent from the Sponsor to the investigator confirming the destruction. It is the responsibility of the investigator to inform the subject of completion of destruction. Any analyses in progress at the time of request for destruction or already performed prior to the request being received by the Sponsor will continue to be used as part of the overall research trial data and results. No new analyses would be generated after the request is received.

In the event that the medical records for the main trial are no longer available (e.g., if the investigator is no longer required by regulatory authorities to retain the main trial records) or the specimens have been completely anonymized, there will no longer be a link between the subject's personal information and their specimens. In this situation, the request for specimen destruction cannot be processed.

7.1.4.2 Blinding/Unblinding

This is an open label trial; there is no blinding for this trial.

7.1.4.3 Calibration of Critical Equipment

The investigator or qualified designee has the responsibility to ensure that any critical device or instrument used for a clinical evaluation/test during a clinical trial that provides important information about inclusion/exclusion criteria and/or safety or efficacy parameters shall be

suitably calibrated and maintained to ensure that the data obtained is reliable and/or reproducible. Documentation of equipment calibration must be retained with the study documentation as source documentation at the trial site.

Critical Equipment for this trial includes:

- ECG machine
- Refrigerated centrifuge
- Freezer for storage of samples
- Refrigerator

7.1.5 Visit Requirements

Visit requirements are outlined in Section 6.0 - Trial Flow Chart. Specific procedure-related details are provided above in Section 7.1 - Trial Procedures.

7.1.5.1 Screening

All screening procedures outlined in Section 6.0 must be performed within 7 days of enrollment into the study. Prior to randomization, potential subjects must be evaluated to determine that they fulfill the entry requirements as set forth in Section 5.1. Only subjects with clinically acceptable results from all screening criteria are to be enrolled in the study. Screening procedures may be repeated after consultation with the Sponsor.

At the Screening visit the following procedures will be performed:

- The investigator or qualified designee shall discuss with the parents(s) or legal guardian of each subject, and with each subject as appropriate, the nature of the study, its requirements, and its restrictions.
- Written informed consent will be obtained from the parent or legal guardian of each subject prior to any study procedures being performed, and a signed copy will be given. Assent will be obtained from minors according to institutional practices.
- The inclusion/exclusion criteria will be reviewed
- A subject identification card will be issued
- Demographic profile
- Complete medical history
- Record all medications taken within the last 14 days
- Screening number will be assigned (after signing of study-specific informed consent)
- Complete physical exam
- Body weight
- Height

- Vital signs (blood pressure, heart rate and temperature)
- Electrocardiogram. A single ECG or telemetry may be used to evaluate QTc for eligibility at the screening visit, however two 12 lead ECGs performed 5 minutes apart must be done at the Baseline Visit to confirm QTc criteria for study eligibility before study drug dosing occurs.
- Blood samples will be collected for evaluation of eligibility criteria and for safety assessments (e.g., pregnancy test, hematology, chemistry & absolute neutrophil count)

